9.3 Others Secondary Efficacy Variables

9.3.1 Number of Days Alive and Ventilator-free at Day 28

First, within subject with a start date filled in the ventilator support form, subjects with at least 12 hours of suspension of ventilation either invasive or non-invasive ventilation will be flagged. Then duration will be calculated within the flagged subject's subset, as below:

- Ventilator-free days = 28-[MAX (End date of invasive ventilation; End date of non-invasive ventilation)] – Date of randomisation + 1].

Subjects who die or are mechanically ventilated longer than this period are assessed as zero ventilator-free days.

Number of ventilator-free days will be described at Day 28.

9.3.2 Mortality at Day 21 and Day 28

The number and proportion of deaths at Day 21 and Day 28 will be presented for both groups.

9.3.3 Number of Days Alive and Free from invasive and Non-Invasive ventilation at Day 21 and Day 28

For Day 21:

First, subjects with at least 12 hours of suspension of ventilation will be flagged by type (i.e. one flag for Non-Invasive, and one for Invasive). Then duration will be calculated within the flagged subject's subsets, as below:

- Invasive ventilation-free days = 21-(End date of invasive ventilation) – Date of randomisation + 1].
- Non-invasive ventilation-free days = 21-(End date of non-invasive ventilation) – Date of randomisation + 1].

If subject never started a non-invasive ventilation then the value will be set to 21 days.

For Day 28:

First, subjects with at least 12 hours of suspension of ventilation will be flagged by type (i.e. one flag for Non-Invasive, and one for Invasive). Then duration will be calculated within the flagged subject's subsets, as below:

- Invasive ventilation-free days = 28-(End date of invasive ventilation) – Date of randomisation + 1].

- Non-invasive ventilation-free days = 28-(End date of non-invasive ventilation) – Date of randomisation + 1].

If subject never started a non-invasive then the value will be set to 28 days.

Subjects who die or are mechanically ventilated longer than this period are assessed as zero ventilator-free days.

9.3.4 Improvement in Severity Status at Day 28 or Discharge

The severity status will be based on the ventilatory parameters form for PaO₂/FiO₂ ratio at baseline and at Day 28 or Discharge (whichever comes first) and on Study Termination form for the death, according to the scale below:

Severity	Variable	Criteria
Mild - 1	PaO ₂ /FiO ₂ Ratio	200 mmHg < PaO ₂ /FIO ₂ ≤ 300 mmHg
Moderate - 2	PaO ₂ /FiO ₂ Ratio	100 mmHg < PaO ₂ /FIO ₂ ≤ 200 mmHg
Severe - 3	PaO ₂ /FiO ₂	Ratio PaO ₂ /FIO ₂ ≤ 100 mmHg
Death - 4	Patient Status	Yes/No

In case of multiple assessments done on same date, the last assessment will be taken into account for the severity status definition.

The severity status, the number and percentage of subjects with an improvement (i.e. a decrease of at least one point of severity) from baseline to Day 28 or Discharge will be summarized. A shift table displaying the severity at baseline and at day 28 or Discharge will also be provided.

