1. INTRODUCTION

1.1 Background information

The 2019 novel coronavirus (SARS-COV-19) has spread rapidly since its recent identification in patients with severe pneumonia in Wuhan, China.

The World Health Organization (WHO) on March 11 declared COVID-19 a pandemic, highlighting the sustained risk of further global diffusion.

The COVID-19 pandemic threatens patients, societies and healthcare systems around the world. Host immunity determines the progress of the disease and its lethality. The associated cytokine storm mainly affects the lungs, leading to acute lung injury of variable severity [1][2][3][4][5]. In epidemiological Chinese studies 17% -29% of hospitalised patients developed ARDS [6][7]. For COVID-19 patients treated on ICU, a mortality rate of 30–70% is expected. For older patients with ARDS, this mortality rate is comparable to other severe pulmonary infections [1][3][5][8][9].

The acute respiratory distress syndrome (ARDS) is a clinical syndrome defined by acute onset hypoxemia (PaO₂:FiO₂ ratio < 300) and bilateral pulmonary opacities not fully explained by cardiac failure or volume overload [10]. The Berlin consensus definition of ARDS, like the American-European Consensus definition that preceded it, has enabled clinicians and researchers alike to prospectively identify patients with ARDS, implement lung protective ventilation strategies, and enrol patients in clinical trials. ARDS remains under-recognized clinically, however; therapies are limited, and mortality remains high [10]. Under-recognition of ARDS may stem in part from the considerable clinical heterogeneity observed among patients who meet standard ARDS criteria. The syndrome may be triggered, for example, by pulmonary or extrapulmonary sepsis, aspiration, trauma, blood product transfusion, or pancreatitis [11]. Pulmonary infiltrates can be focal or diffuse. Hypoxemia can range from mild to severe, and duration of respiratory failure can be brief or prolonged. Many of these clinical variations may reflect underlying biological differences between ARDS patients that are now recognized as important drivers of treatment response and ultimate outcomes [12].

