4.2 Inclusion Criteria

Participants are eligible to be included in the study if the following criteria apply:

1. Male or female ≥ 18 and ≤ 80 years of age
2. Informed consent for participation in the study (*refer to [section 15](#) for detailed informed consent procedure*)
3. Positive SARS-COV-19 rt-PCR before randomisation
4. PaO₂/FiO₂ ratio < 150 mmHg
5. Lung compliance ≤ 45 ml/cmH₂O
6. Intubated and artificially ventilated less than 48 hours before the first poractant alfa administration

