7. STUDY PLAN

7.1 Study Schedule

	ICU stay period					ICU discharge	Last FUP
Poractant alfa treated group	Screening ⁷	Day 1 (Randomisation)	Day 2	Day 3	Day 4 – 27	Day X	Day 28
		Before randomisation/treatment and 6-12-24h after each administration up to 72 hours			Every 24h till ICU discharge	Whenever it occurs	
Control group	Screening	Time 72 h			Day 4 – 27	Day X	Day 28
		Before randomisation and at 6, 12, 24, 30, 36, 48, 54, 60, 72 h since randomisation			Every 24h till ICU discharge	Whenever it occurs	
Assessments							
Informed consent	X						
Inclusion and exclusion criteria	X						
Demography	X						

Clinical Study Code No.: CLI-050000-04	Version No.: 4.0
EUDRACT No.: 2020-002632-75 – IND No: 153286	Date: 02 MAR 2021

Poractant alfa treated group	ICU stay period					ICU discharge	Last FUP
	Screening ⁷	Day 1 (Randomisation)	Day 2	Day 3	Day 4 – 27	Day X	Day 28
		Before randomisation/treatment and 6-12-24h after each administration up to 72 hours			Every 24h till ICU discharge	Whenever it occurs	
Control group	Screening	Time 72 h			Day 4 – 27	Day X	Day 28
		Before randomisation and at 6, 12, 24, 30, 36, 48, 54, 60, 72 h since randomisation			Every 24h till ICU discharge	Whenever it occurs	
Vital signs (blood pressure, heart rate)	X	Once Treated group: 24 - 48 - 72h post start of treatment Control group: 24 - 48 - 72h post randomisation			X	X	X
Full physical examination including height and weight	X						
Medical history (SARS COVID-19 ADRS, past and current relevant medical conditions)	X						
Arterial Blood Gas (ABG) Analysis ¹	X (If the screening assessment is done just before randomization no need to repeat the assessment)	Treated group: Before randomisation and 6-12-24h after each administration up to 72 hours Control group: Before randomisation and at 6, 12, 24, 30, 36, 48, 54, 60, 72h since randomisation			Every 24h	X	Once if not discharged from ICU
Respiratory support assessment Ventilator parameters ²	X (If the screening assessment is done just before randomization no need to repeat the assessment)	Treated group: Before randomisation and 6-12-24h after each administration up to 72 hours Control group: Before randomisation and at 6, 12, 24, 30, 36, 48, 54, 60, 72h since randomisation			Every 24h	X	Once if not discharged from ICU

Clinical Study Code No.: CLI-050000-04	Version No.: 4.0
EUDRACT No.: 2020-002632-75 – IND No: 153286	Date: 02 MAR 2021

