7.4 Handling of Missing Data

In general, except as described below, missing data will not be imputed.

The number of subjects with missing data will be presented under a “Missing” category. Unless otherwise stated, missing values will not be included in the denominator count when calculating percentages.

When quantitative variables are being summarized, only the non-missing values will be evaluated for calculating summary statistics.

Other critical missing data, if any, will be discussed during the review of the data before database lock. Decisions will be fully documented in the Data Review Report.

Medications: Missing/Incomplete Date

In case of missing or incomplete dates not directly allowing allocation to any category of medications, a worst-case allocation will be done according to the available parts of the start and the stop dates. The medications will be allocated to the first category allowed by the available data, according to the following order:

1. Concomitant medication;
2. Maintained medication;
3. Prior medication.

Procedures: Missing/Incomplete Date

In case of missing or incomplete dates not directly allowing allocation to any category of procedure, a worst-case allocation will be done according to the available parts of the start and the stop dates. The procedure will be allocated to the first category allowed by the available data, according to the following order:

1. Concomitant procedure;
2. Maintained procedure;
3. Prior procedure.

Adverse Events (AEs): Missing/Incomplete Date

In case of missing or incomplete date/time not directly allowing allocation to any of the category of AEs, a worst-case allocation will be done according to the available parts of the start and the stop dates/times. The AE will be allocated to the first category allowed by the available data, according to the following order:

1. Treatment emergent;
2. Pre-treatment.

Adverse Events (AEs): Missing Severity

In case of missing severity, the severity will not be imputed and will be reported as “Missing”. For the table of TEAEs by maximum severity, the maximum severity will be considered as the maximum of the non-missing severities for the relevant subject and preferred term.

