7.9 Definitions

7.9.1 Baseline

Baseline is defined as the last non-missing value available before randomisation (for control group)/first treatment dose (for poractant alfa group).

Change from baseline will be derived as follows:

Assessment value at the timepoint - Assessment value at baseline

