Table 14.2.7.1	Summary of Proportion of Subjects with Improvement in Severity Status at Day 28/Discharge (Intention-To-Treat)	TPT006	
 - Summarize the Severity Status (Mild -1, Moderate -2, Severe -3 and Death - 4) at Baseline and Day 28/Discharge and then the Proportion of Subjects with an Improvement in Severity Status at Day 28/Discharge. - Do not present 'At Any timepoint' line. 	Add the footnotes: [1] Mild : 200 $\text{mmHg} < \text{PaO}_2/\text{FiO}_2 \leq 300$ mmg Moderate: 100 $\text{mmHg} < \text{PaO}_2/\text{FiO}_2 \leq 200$ mmg Severe: Ratio $\text{PaO}_2/\text{FiO}_2 \leq 100 \text{ mmHg}$ [2] An improvement is defined by a decrease of at least one point between baseline and Day 28/Discharge Source: Listing 16.2.6.2-b
Table 14.2.7.2	Severity Status: Shift from Baseline to Day 28/Discharge (Intention-To-Treat)	EGT005	
 - Do not present the 'Visit' line. - Display the following categories at Baseline and at Day 28/Discharge :Mild - 1, Moderate - 2, Severe - 3, Death - 4 	Add the footnotes [1] Mild : 200 $\text{mmHg} < \text{PaO}_2/\text{FiO}_2 \leq 300$ mmg Moderate: 100 $\text{mmHg} < \text{PaO}_2/\text{FiO}_2 \leq 200$ mmg Severe: Ratio $\text{PaO}_2/\text{FiO}_2 \leq 100 \text{ mmHg}$ Source: Listing 16.2.6.2-b

Table Number	Table Title	Template Code	Notes	Footnotes/Source Listing Number
Table 14.2.8	Summary of Actual Values and Change from Baseline in PaO ₂ /FiO ₂ Ratio at Each Timepoint (Intention-To-Treat Set)	TPT001	
 - Overall column should not be displayed. - Remove '95% CI for Mean', 'n geometric', 'Geometric mean' categories. 	Add the footnote: [1] Duplicated data reported twice at 2 different timepoints are reported at the first occurrence for post dose/post randomisation and at the last occurrence for pre dose/pre randomisation. Source: Listing 16.2.6.2-a
Table 14.2.9	Summary of Proportion of Subjects with PaO ₂ /FiO ₂ Ratio Improvement >20% Compared to Baseline at Each Timepoint (Intention-To-Treat Set)	TPT006	
 - Do not present 'At Any timepoint' line. 	Add the footnote: [1] Duplicated data reported twice at 2 different timepoints are reported at the first occurrence for post dose/post randomisation and at the last occurrence for pre dose/pre randomisation. Source: Listing 16.2.6.2-a

Table Number	Table Title	Template Code	Notes	Footnotes/Source Listing Number

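### The severity scale has no level above PaO2/FiO2 300 mmHg, so a survivor above 300 at the Day 28/Discharge assessment cannot be counted as improved

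*SAP*

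**What the plan says.** The scale is the same in Protocol section 8 and SAP 4.1.2.2 and 9.3.4: Mild (1) is a ratio above 200 and up to 300 mmHg, Moderate (2) above 100 and up to 200, Severe (3) up to 100, and Death is 4. SAP 9.3.4 summarises "the number and percentage of subjects with an improvement (i.e. a decrease of at least one point of severity) from baseline", assessed at Day 28/Discharge. The shift table, Table 14.2.7.2 in SAP 16.1, repeats the four levels: "Display the following categories at Baseline and at Day 28/Discharge :Mild - 1, Moderate - 2, Severe - 3, Death - 4". The footnotes to Table 14.2.7.1 give the same cut-offs.

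Entry requires a "ratio < 150 mmHg" (Protocol 4.2). Protocol 1.1 describes ARDS by a "ratio < 300) and bilateral pulmonary opacities not fully explained by cardiac failure".

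On missing data, SAP 7.4 says "The number of subjects with missing data will be presented under a" Missing category and that, unless otherwise stated, "missing values will not be included in the denominator count when calculating percentages". SAP 7.8 sets the same default denominator. Neither section mentions an observed ratio that falls outside the scale.

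**The concern.** With entry below 150 mmHg, a patient normally starts at score 2 or 3. The scale credits recovery to 201–300 mmHg but has no place for recovery beyond 300, which on the protocol's own description is where oxygenation has left the ARDS range. Improvement is a fall in score, and without a second score no fall can be derived. Deaths, by contrast, are always scored.

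The programmer must therefore choose how to treat these survivors, and the choice changes the percentage. The model-based comparison in Protocol 12.3.5 was withdrawn in SAP section 12, so the summary percentage and the shift table are the whole reported result for this endpoint.

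A smaller matter of the same kind affects the responder percentage for a ratio improvement of more than 20% (SAP 9.3.6). Earlier deaths count as failures at every later timepoint, but the ratio is followed only until ICU discharge and no denominator is stated. The 20% boundary is also written differently in SAP 9.3.6 and in Listing 16.2.6.2-a.

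**Working it through.** The documents give no expected rate for this endpoint. The only design figure is 84% power for the primary endpoint (42 vs 28, difference 4, SD 5.5, two-sided 0.05). It reproduces at 83.6% with the noncentral t and 84.6% with the normal approximation, and has no bearing on this point.

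**1. The scale applied literally**

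| Baseline → Day 28/Discharge (mmHg) | Scores | Improved? |
|---|---|---|
| 140 → 250 | 2 → 1 | yes |
| 140 → 300 | 2 → 1 | yes |
| 140 → 301 | 2 → none | cannot be derived |
| 90 → 300 | 3 → 1 | yes |
| 90 → 301 | 3 → none | cannot be derived |

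**2. Effect within one arm.** Let p be the share truly improved, including those above 300, and r the share of the arm above 300 at the assessment. Assume everyone above 300 started at a scored level.

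- Treated as missing and dropped: reported share = (p − r)/(1 − r).
- Treated as not improved and kept: reported share = p − r.

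With p = 50% (assumed):

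| r | Dropped | Kept |
|---|---|---|
| 10% | 0.40/0.90 = 44.4% | 40% |
| 20% | 0.30/0.80 = 37.5% | 30% |
| 30% | 0.20/0.70 = 28.6% | 20% |

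The shortfall is r(1 − p)/(1 − r) if dropped and r if kept. It is above zero whenever r > 0, except under the dropped reading when everyone improves (p = 100%).

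**3. Effect on the difference between arms.** If r is equal in both arms, dropping multiplies the true difference by 1/(1 − r), for example 1.11 at r = 10% and 1.43 at r = 30%; keeping leaves it unchanged. If r differs, anything can happen. The counts below are assumed, at the planned 42 vs 28, in the order dead / above 300 / improved to 300 or less / not improved.

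| Counts | With a level above 300 | Dropped | Kept |
|---|---|---|---|
| A: 13/15/10/4 vs 9/4/8/7 | 25/42 = 59.5% vs 12/28 = 42.9% (+16.7) | 10/27 = 37.0% vs 8/24 = 33.3% (+3.7) | 10/42 = 23.8% vs 8/28 = 28.6% (−4.8) |
| B: 13/12/12/5 vs 13/8/4/3 | 24/42 = 57.1% vs 12/28 = 42.9% (+14.3) | 12/30 = 40.0% vs 4/20 = 20.0% (+20.0) | 12/42 = 28.6% vs 4/28 = 14.3% (+14.3) |
| C: 13/13/8/8 vs 9/4/8/7 | 21/42 = 50.0% vs 12/28 = 42.9% (+7.1) | 8/29 = 27.6% vs 8/24 = 33.3% (−5.7) | 8/42 = 19.0% vs 8/28 = 28.6% (−9.5) |

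The same counts can shrink, inflate, preserve or reverse the difference, depending on a rule that the SAP does not state.

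**4. The 20% responder percentage.** If the general rule in SAP 7.4 is applied, live discharges drop out while deaths stay in. Assumed late timepoint: 13 dead, 19 discharged alive and 10 in ICU (5 responding), against 9, 7 and 12 (6 responding). The percentages are 5/(13 + 10) = 21.7% vs 6/(9 + 12) = 28.6%. Mortality is similar (13/42 = 31% vs 9/28 = 32%), and the first arm has more live discharges (19/42 = 45% vs 7/28 = 25%). On the boundary, SAP 9.3.6 puts exactly 20% in the lower class; Listing 16.2.6.2-a puts it in the upper class.

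**The case against.** The strongest reply is that little is lost. The endpoint is a non-key secondary one, with no model or test after SAP sections 7.5 and 12, so no alpha or power is touched. Listing 16.2.6.2-a shows each patient's ratio by timepoint, so a reader can separate patients above 300 from those with no value. Tables 14.2.8 and 14.2.12 show part of the recovery. All of this stands, and it limits the matter to the summary percentage and the shift table.

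Some stronger readings are tempting but go beyond the documents:

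- **That a patient who ever passes 300 can never count.** Only the Day 28/Discharge value is used. A patient who passes 300 earlier and is at 201–300 then scores Mild and counts as improved.
- **That patients above 300 certainly leave the denominator.** SAP 7.4 and 7.8 concern missing values, and a ratio of 320 is observed. Dropping it is an inference.
- **That the comparison is biased in a known direction.** The counts above are chosen to show what is possible. No document supports those imbalances.
- **That many patients start at Mild and so have no room to improve.** "Baseline is defined as the last non-missing value available before randomisation" for controls, or before the first dose in the treated arm, and the ratio is repeated unless screening was close to randomisation ("If the screening assessment is done just before randomization no need to repeat the assessment"). A rise above 200 between entry and baseline is possible, but nothing suggests that it is common.
- **That the 20% responder percentage fails as an all-patient rate.** It is defined only until ICU discharge, so the documents do not promise such a rate. The defect is an unstated denominator.

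**Conclusion.** The point holds for the severity endpoint. Followed literally, the scale leaves a survivor above 300 mmHg at Day 28/Discharge unscored, so the best oxygenation result cannot enter the numerator under either reading of the denominator. With p = 50% and r between 10% and 30%, both assumed, the reported share falls to between 44.4% and 28.6% if such patients are dropped, or between 40% and 20% if they are kept. The effect on the difference between arms is unknown in size and direction because the documents give no rates above 300. No conclusion about the primary or key secondary endpoint is affected. It should be corrected because the correction is cheap and the present rule gives a wrong answer for recovered patients. The 20% boundary mismatch and the unstated denominator in SAP 9.3.6 are minor.

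**What to change.** Add level 0, PaO2/FiO2 above 300 mmHg, to SAP 4.1.2.2 and 9.3.4, Tables 14.2.7.1 and 14.2.7.2, and the severity rows of Listing 16.2.6.2-b. Count a move to level 0 as improvement. Put only survivors with no ratio under Missing.

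The scale is defined in the protocol, the SAP is final, and this open-label trial has closed recruitment. So report the four-level percentage beside the new one, with its denominator stated, and record the addition in SAP section 12 as a late change.

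Minor: use the SAP 9.3.6 boundary in Listing 16.2.6.2-a. In Table 14.2.9, state the denominator and show by arm, at each timepoint, the numbers in ICU with a value, discharged alive, dead and otherwise missing.

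The cost is SAP wording, one derivation, three tables and two listings. No new data or imputation is needed: the ratio is already scheduled at ICU discharge (Protocol 7.1.4) and at Day 28 for patients still in hospital (Protocol 7.1.5).

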9.3.5 Change from Baseline in PaO₂/FiO₂ Ratio at each Timepoint After Treatment

Actuals values and change from baseline in PaO₂/FiO₂ ratio at 6 and 12 hours following each treatment medication administration and then each 24 hours till the subject is discharged from the ICU in the poractant alfa group and similar timepoints in the control group (defined as 6 and 12 hours post randomization for Day 1, 30 and 36 hours post randomization for Day 2 and 54 and 60 hours post randomization for Day 3 and then each 24 hours till the subject is discharged from the ICU) will be described by treatment group.

A graph displaying the mean value and SD for each timepoint will be also provided for each treatment group.

9.3.6 Percentage of Subjects with PaO₂/FiO₂ Ratio Improvement of >20% Compared to Baseline at each Timepoint After Treatment

The number and percentage of subjects with PaO₂/FiO₂ ratio improvement of >20% compared to baseline at 6 and 12 hours following each dose administration and then each 24 hours till the subject is discharged from the ICU in the poractant alfa group and similar timepoints in the control group (defined as 6 and 12 hours post randomization for Day 1, 30 and 36 hours post

randomization for Day 2 and 54 and 60 hours post randomization for Day 3 and then each 24 hours till the subject is discharged from the ICU) will be described.

Subjects who die before the analysis timepoint will be considered as a failure.

Notes:

- % change in $\text{PaO}_2/\text{FiO}_2$ ratio = $[(\text{Value} - \text{baseline})/\text{baseline}] \times 100$
- If % change in the ratio $>20\%$, then $\text{PaO}_2/\text{FiO}_2$ ratio improvement = ' $>20\%$ ', else ' $\leq 20\%$ '

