4.1 Efficacy Variables

4.1.1 Primary Efficacy Variable

The primary efficacy variable is the number of days alive and ventilator-free defined as the number of days the subjects is alive and not receiving mechanical ventilation over the **21 days** following randomisation.

Mechanical ventilation is defined as invasive and non-invasive. Subject is defined as free of mechanical ventilation after 12 hours from the suspension of either invasive or non-invasive ventilation. Subjects who die or are mechanically ventilated longer than this period are assessed as zero ventilator-free days.

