4.1.2 Secondary Efficacy Variables

4.1.2.1 Key Secondary Efficacy Variable

- Percentage of subjects alive and free of respiratory failure (i.e., need for mechanical ventilation, ECMO, non-invasive ventilation, or high-flow nasal cannula oxygen delivery) **at Day 28**.

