4.2 Safety Variables

- Adverse events (AEs).
- Laboratory parameters.
- Vital signs (blood pressures and pulse rate).

5 Sample Size

A total of 70 subjects will be randomised in the study with a ratio 3:2 (i.e. 42 subjects randomised to the poractant alfa group and 28 in the control group). Assuming subjects in the control arm being free from ventilation on average 1 week (i.e. 7 days), this sample size achieves 84% power to detect a difference of 4 days (i.e. on average 11 ventilation-free days for subjects treated with poractant alfa), assuming a standard deviation of 5.5 and a two-sided significance level (alpha) of 0.05 using a two-sample t-test.

6 Analysis Set

The definition of the analysis set is summarized below. A final agreement on the subjects to be included in or excluded from the analysis set will be reached during the review of the data

before database lock. Inclusions and exclusions from the analysis set will be fully documented in the Data Review Report.

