7.2 Intercurrent Events

Death and Early discontinuation from study drug can be anticipated as intercurrent events:

- Death will be incorporated as a failure outcome for binary endpoints using composite strategy;
- Early discontinuation from study drug will be handled using treatment policy strategy: all data collected after discontinuation from study drug till Day 28 or death will be included;
- Change in respiratory parameters will be analysed using while-alive strategy.

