Listing 16.2.6.1	Ventilatory Support (Intention-To-Treat Set)		
The following columns will be presented:
 
 - Subject ID - Randomized Treatment - Actual Treatment - Ventilator Type - Start Date/Time [Day] - Stop Date/Time [Day] or Ongoing - Duration of Ventilatory Support (Days) – displayed by Type of Support (Invasive or Not Invasive) - Overall Duration of Ventilator Support 	Add the footnotes: [1]: Duration of ventilatory support have been calculated as the difference between end date and start date +1. [2]: Overall duration of ventilatory support has been calculated as the difference between the maximum end date (between invasive and non-invasive ventilation) and start date +1.

Listing Number	Listing Title	Template Code	Notes	Footnotes
Listing 16.2.6.2-a	Ventilatory Parameters by Timepoint (Intention-To-Treat Set)	VSL002	
 - Remove 'Analysis Period' - Display 'Assessment date/Time [Study Day]' instead of 'Assessment date/time [study day / study day in period]' - Do not display [H] flag in Change from baseline column - Skip the last column (Change from pre-dose) - In Test <Unit> column, display: 
 - FiO2 (%) - Mean Arterial Pressure (mmHg) - Dynamic Compliance (ml/cmH₂O) - Static Compliance (ml/cmH₂O) - PaO₂/FiO₂ Ratio - Tidal Volume (ml/kg BW) - Respiratory Rate (/min) - Peak Inspiratory Pressure - PIP (cmH₂O) - Plateau Pressure (cmH₂O) - Positive End-Expiratory Pressure - PEEP (cmH₂O) - Blood Flows (L/min) - Sweep Gas Flows (L/min) - Add a last column displaying PaO₂/FiO₂ Ratio Improvement (<20%, >=20% or death) 	Add the footnotes: [1]: Baseline=Y flags baseline value [2]: Use=Y: included in the analysis [3] Duplicated data reported twice at 2 different timepoints are reported at the first occurrence for post dose/post randomisation and at the last occurrence for pre dose/pre randomisation.

Listing Number	Listing Title	Template Code	Notes	Footnotes

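### ECMO started after randomisation has no rule in the PaO2/FiO2 responder and severity-improvement endpoints, so a patient alive on ECMO can be scored as improved

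*SAP*

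**What the plan says.** **Intercurrent events.** SAP 7.2 and Protocol 12.3 name the same two: "Death and Early discontinuation from study drug can be anticipated as intercurrent events". Death is a composite failure for binary endpoints, and changes in respiratory parameters are analysed while the patient is alive. ECMO is not mentioned.

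**PaO2/FiO2 responder (SAP 9.3.6).** Each subject is classified by the percentage change in the measured ratio, with one override: "Subjects who die before the analysis timepoint will be considered as a failure". SAP Listing 16.2.6.2-a mirrors this, with two ratio categories and death.

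**Severity improvement (SAP 9.3.4; Protocol 8).** The score is one of three PaO2/FiO2 bands, or death. There is no ECMO category.

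**Data used (SAP 7.12).** Nothing in the database is left out of the analyses.

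**Key secondary endpoint (SAP 4.1.2.1 and 9.2; Protocol 8 and 12.3.4.1).** Here ECMO is handled. Respiratory failure at Day 28 means "need for mechanical ventilation, ECMO, non-invasive ventilation, or high-flow nasal cannula oxygen delivery".

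**Ventilator-free days (SAP 4.1.1 and 9.1).** "Mechanical ventilation is defined as invasive and non-invasive". ECMO is not named.

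**Entry.** Protocol 4.3 excludes patients on ECMO. The protocol outline forbids no concomitant treatment afterwards.

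**The concern.** ECMO oxygenates blood outside the body, so a PaO2/FiO2 ratio measured during it no longer describes the lungs alone. A patient who worsens until ECMO is started, and survives to the assessment, can show a better ratio because of the circuit. Under 9.3.6 and 9.3.4 that patient counts as a success. The trial's own key secondary definition would call the same patient, if still on ECMO at Day 28, a respiratory failure.

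The direction of the bias depends on which arm has more ECMO. If it is the control arm, a benefit of poractant alfa is partly hidden. If it is the treated arm, a harm is partly hidden. With the planned models dropped, these percentages are the only evidence on the two endpoints.

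**Working it through.** **1. The plan's own figure.** Inputs (SAP section 5): "42 subjects randomised to the poractant alfa group and 28 in the control group"; "this sample size achieves 84% power to detect a difference of 4 days"; "assuming a standard deviation of 5.5 and a two-sided significance level (alpha) of 0.05 using a two-sample t-test".

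- Standard error = 5.5 × √(1/42 + 1/28) = 1.342; 4/1.342 = 2.98.
- Power = 83.6% by noncentral t with 68 degrees of freedom, or 84.6% by the normal approximation.

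The stated 84% is reproduced and not in dispute. It is used here only for the arm sizes.

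**2. Applying the rules to a patient on ECMO.** The values are assumed, because the documents give none.

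- Baseline PaO2 80 mmHg at FiO2 0.80: ratio = 80/0.80 = 100, which is Severe (3).
- More than 20% improvement needs a ratio above 120. At unchanged FiO2 that is PaO2 above 0.80 × 120 = 96 mmHg.
- PaO2 97 mmHg on ECMO: ratio = 97/0.80 = 121.25, a change of +21.25%. SAP 9.3.6 scores a responder.
- If that is the Day 28 or Discharge value, the band is Moderate (2). The score falls from 3 to 2, and SAP 9.3.4 scores an improvement.

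No fall in ventilator FiO2 is needed, and no rule in either section changes the result unless the patient dies.

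**3. Size per misclassified patient.** Scoring one patient as improved instead of not improved moves the arm percentage by 100/n points.

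| Total (3:2) | Treated n | Points | Control n | Points |
|---|---|---|---|---|
| 70 (planned) | 42 | 2.4 | 28 | 3.6 |
| 40 (assumed) | 24 | 4.2 | 16 | 6.25 |
| 20 (assumed) | 12 | 8.3 | 8 | 12.5 |

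SAP section 12 says recruitment closed below 70 without giving the number, so the lower rows show a range. SAP 7.8 takes non-missing values as the denominator, so the shift at a given timepoint can be larger than shown.

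**4. Ventilator-free days.** SAP 9.1 and 9.3.1 count days after the later of the invasive and non-invasive end dates, and death scores zero. ECMO days can be credited only if the patient survives, both forms of ventilation have ended for good, and the Ventilatory Support form does not record ECMO as invasive support. If all three hold, crediting 5 to 20 days (assumed) instead of 0 moves the arm mean by:

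- treated: 5/42 = 0.12 to 20/42 = 0.48 days;
- control: 5/28 = 0.18 to 20/28 = 0.71 days.

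The planned difference is 4 days.

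**The case against.** **ECMO is already a failure in this trial.** A reader might infer that the plan never treats ECMO as a failure. It does so in the key secondary endpoint, and a patient on ECMO in the ICU at Day 28 also fails the endpoint of being alive and out of ICU (SAP 9.3.9). This limits the point to 9.3.6 and 9.3.4 but leaves the gap there.

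**Days on ECMO may not count as ventilator-free.** A reader might infer that they do. The documents do not establish it. SAP 9.2 derives the endpoint that includes ECMO from the Ventilatory Support form across all ventilator types. SAP 9.3.8 names a form subtype for invasive mechanical ventilation, so ECMO may be another invasive subtype. The form is not in the documents, and the last-end-date formula narrows the case further. This part stands only as a condition.

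**The number affected is unknown.** It could be zero. Even an assumed cumulative ECMO rate would overstate the effect, because the responder endpoint is scored per timepoint and severity once. Only a patient on ECMO at that assessment with a sufficiently raised ratio matters. This stands, so only the effect per patient is given.

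**The endpoints measure different things.** Support status at Day 28 and gas exchange at a timepoint can differ without formal contradiction. That is fair. The weakness is that the ratio is read as improvement when part of the oxygenation comes from the circuit.

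**No inference is affected.** SAP 7.5 and section 12 make everything descriptive, so a reading that a test or the power is compromised is not supported. The percentages can still mislead.

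**ECMO may be a remnant of the removed cohort.** The SAP version history shows the cohort removed and the key secondary endpoint added in the same update, so its mention of ECMO is deliberate. The blood and sweep gas flows in Listing 16.2.6.2-a may indeed be left over, and they do not prove that ECMO dates are captured.

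**Conclusion.** The point holds for two binary endpoints. In SAP 9.3.6 and 9.3.4 only death overrides the measured ratio, so a patient alive on ECMO can be scored as improved. Each such patient at a given timepoint shifts the arm percentage by 2.4 or 3.6 points at the planned size. The shift is 8.3 or 12.5 points if only 20 patients were randomised (assumed).

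This rests on two assumptions that the documents do not settle: that some patients started ECMO, and that the circuit raised their measured ratio enough to cross the threshold. For ventilator-free days the concern is conditional on how the form codes ECMO, and the effect per patient is below one day. The change is worth making because it is small and brings the two endpoints into line with the trial's own definition of respiratory failure.

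**What to change.** 1. **SAP 7.2.** Add ECMO as an intercurrent event, with a composite strategy for these two endpoints. A subject on ECMO at the assessment timepoint counts as not improved in 9.3.6 and 9.3.4. Use current status in both, so that a patient weaned from ECMO is again judged on the measured ratio.
2. **Continuous respiratory parameters.** Keep the planned summaries of change in PaO2/FiO2, FiO2 and ventilator parameters. Add the number on ECMO by timepoint and arm. Show off-ECMO values only as a supplementary summary, because excluding on-ECMO values removes the sickest patients.
3. **Ventilator-free days (9.1, 9.3.1 and the invasive part of 9.3.3).** State whether the Ventilatory Support form codes ECMO as invasive support. If it does not, include the ECMO end date when taking the latest end date. Do not apply this to days free from non-invasive ventilation, which concern one specific type of support.
4. **Record.** Note the change in SAP section 12, since the protocol defines these endpoints. If the database is already locked, SAP section 1 allows the deviation to be explained in the study report, with the revised scoring shown as a sensitivity summary.

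**Cost.** Slightly fewer responders, minor programming, and a check that ECMO start and stop dates are captured.
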